11.4.3 Secondary Analyses

The secondary endpoints are time to improvement of at least 2 points on the WHO 7-point outcome scale, the proportion of subjects with an ALI (defined by PaO₂/FiO₂ ratio of <300mmHg) within 14 days after enrolment and the proportion of participants alive and not having required invasive or non-invasive ventilation at 14 days after enrolment. They will be tested only after a significant test of the primary endpoint (a priori ordered hypotheses), therefore, no alpha adjustment is necessary.

Quantitative secondary study parameters will be described based on their mean, standard deviation, median, IQR, minimums and maximums and portrayed by Kaplan-Meier plots and compared with the logrank test.

Qualitative secondary study parameters will be analyzed by means of absolute and relative frequencies. Pairwise Chi-Square tests will be carried out in order to compare each of the active treatments to placebo. Moreover, 95% confidence intervals for the treatment differences will be calculated.

Other outcomes of interest will be analyzed by means of descriptive and exploratory statistics.

The analyses will be carried out by the trial biostatistician.

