Study Centre(s):	Multi-national study (it is planned to recruit patients in approximately 4-6 centers in Switzerland, Brazil and Mexico)
Statistical Considerations:	
Detailed methodology for statistical analyses of the data collected in this trial will be documented in a Statistical Analysis Plan.
 
Full Analysis Set/Intent-to-Treat Population: The FAS/ITT Population is defined as all patients who are randomly allocated to a study arm. Statistical analyses will be based on the treatment arm to which the patient was allocated.
 
Safety Population: The Safety Population is defined as all patients who received at least one dose of conestat alfa.
 
The primary endpoint WHO 7-point outcome scale at day 7 will be analyzed by nonparametric logrank test stratified by its baseline values with two-sided α-level of 5 %.
 
The secondary endpoint is time to improvement of at least 2 points. It will be tested only after a significant test of the primary endpoint (a priori ordered hypotheses), therefore, no alpha adjustment is necessary.
 
Furthermore, 95% confidence intervals will be determined, and the results will be presented graphically by means of box-and-whisker plots.
 
Time to event (e.g. death, virological clearance, defervescence) will be displayed by Kaplan-Meier plots and compared with a logrank test. Appropriate statistical tests will be used for the analysis of other outcomes of interest and will be detailed in the statistical analysis plan prior to unlocking of the study database.

GCP Statement:	This study will be conducted in compliance with the protocol, the current version of the Declaration of Helsinki, the ICH-GCP or ISO EN 14155 (as far as applicable) as well as all national legal and regulatory requirements.

ABBREVIATIONS

Provide a list of abbreviations used on the protocol - to be completed

AE	Adverse Event
BASEC	Business Administration System for Ethical Committees, (https://submissions.swissethics.ch/en/)
CA	Competent Authority (e.g. Swissmedic)
CEC	Competent Ethics Committee
CS	Complement system
C1INH	C1 esterase inhibitor
COVID-19	Coronavirus disease 2019
CRF	Case Report Form
ClinO	Ordinance on Clinical Trials in Human Research (in German: KlinV, in French: OClin, in Italian: OSRUm)
eCRF	Electronic Case Report Form
CTCAE	Common terminology criteria for adverse events
DSUR	Development safety update report
GCP	Good Clinical Practice
IB	Investigator's Brochure
Ho	Null hypothesis

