5.2 Secondary Outcomes

The secondary endpoints will evaluate the effect of conestat alfa treatment in addition to SOC treatment relative to only SOC treatment on disease progression as measured by

- Time to clinical improvement (time from randomisation to an improvement of two points on the seven-category WHO ordinal scale or live discharge from hospital, whichever came first) within 14 days after enrolment.
- Proportion of participants alive and not having required invasive or non-invasive ventilation at 14 days after enrolment.

- Proportion of subjects with an ALI (defined by PaO₂/FiO₂ ratio of ≤300mmHg) within 14 days after enrolment

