11.4.2 Primary Analysis

The primary endpoint WHO 7-point outcome scale at day 7 will be analyzed by nonparametric logrank test stratified by its baseline values with two-sided α -level of 5 %.

Two adaptive interim analyses after 40 and 80 patients are planned according to the Pocock adjusted levels $\alpha_p = 0.0221$. The results of the sequential groups are combined by the inverse-normal-method (Lehmacher, Wassmer, 1999). There are no prespecified futility margins, but the DSMB can stop the study in the case of insufficient interim results.

Furthermore, 95% confidence intervals will be determined, and the results will be presented graphically by means of box-and-whisker plots.

The analyses will be carried out by the trial biostatistician.

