11.4.4 Interim analyses

Two interim analyses after 40 and 80 patients are planned according to the Pocock adjusted levels $\alpha_p = 0.0221$. Based on the results of an interim analysis the sample size can be adjusted (Lehmacher, Wassmer, 1999). There are no prespecified futility margins, but the DSMB can recommend stopping the study in the case of insufficient interim results.

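### Gating on the primary endpoint does not by itself justify testing three secondary endpoints without alpha adjustment in a three-look design; the protocol fixes no binding order, stopping rule or level for them

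*Protocol*

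**What the plan says.** Section 11.4.3 names time to improvement, then acute lung injury (ALI), then being alive without ventilation at day 14. It continues: "They will be tested only after a significant test of the primary endpoint (a priori ordered hypotheses), therefore, no alpha adjustment is necessary". It gives no numerical level for these tests.

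The statistical part of the synopsis attaches the same rule, with the same remark about ordered hypotheses, to a single endpoint: "The secondary endpoint is time to improvement of at least 2 points".

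Section 5.2 (likewise 4.3 and the synopsis list of outcomes) has all three endpoints, but with "Proportion of participants alive and not having required invasive or non-invasive ventilation at 14 days after enrolment" second and ALI third.

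For the primary endpoint, section 11.4.2 specifies a "nonparametric logrank test stratified by its baseline values with two-sided α -level of 5" percent. On the looks, section 11.4.4 says: "Two interim analyses after 40 and 80 patients are planned according to the Pocock adjusted levels", the level being 0.0221. Section 11.4.2 adds: "The results of the sequential groups are combined by the inverse-normal-method". On intervals it says: "Furthermore, 95% confidence intervals will be determined". Section 11.4.3 also promises 95% intervals for treatment differences.

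**The concern.** A gate on the primary protects the secondary endpoints as a group only while the primary null hypothesis is true. Once the primary effect is real, the gate opens with high probability and the secondaries need protection of their own. A fixed sequence provides it, but only with one stated order and a rule that testing stops at the first failure. The protocol states neither. The remark about ordered hypotheses may mean only that the primary comes before the secondaries. That is the sense it must have in the synopsis, where it refers to one secondary.

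The claim also passes over the group-sequential design. The primary can succeed at any of three looks, so each secondary is tested at a look chosen by the data, and the protocol gives no level for that.

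At stake is the error rate of any secondary claim made after a positive primary result. There could also be a published interval that disagrees with the formal decision on the primary.

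**Working it through.** **Inputs from the protocol.** Overall two-sided alpha 0.05; looks after 40 and 80 patients and at the end (120); 0.0221 per look; inverse-normal combination (11.4.2, 11.4.4); SD 1.5, effect 1 point, 80 + 40 patients (11.2). **Assumed, because the protocol gives none:** correlations between the endpoints, varied from 0 to 1; 5% as the level for each secondary; equal information per stage.

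**1. The plan's own figure.** For three equally spaced looks the Pocock critical value is 2.2895, a nominal two-sided level of 0.02205, which rounds to 0.0221. Using 0.0221 (critical value 2.2886) at all three looks gives an overall alpha of 5.0%. The stated level is correct for three looks.

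**2. Gate only, order not binding.** With the primary effect real and three true secondary nulls each tested at 5%:
- Independent: 1 − (1 − 0.05)³ = 1 − 0.857375 = 14.3%.
- By simulation at mutual correlation 0.3 / 0.5 / 0.7 / 0.9: 13.6% / 12.5% / 10.9% / 8.4%.

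**3. Binding order, each tested once at 5% at the look where the primary first crosses.** Only the first true null in the sequence can cause an error, so one secondary is enough. Maximum over primary effects, by simulation:

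| Correlation with primary | Two-sided error | Error in the favourable direction |
|---|---|---|
| 0 | 5.0% | 2.5% |
| 0.5 | 5.0% | 2.9% |
| 0.7 | 5.0% | 3.3% |
| 0.9 | 5.0% | 4.0% |
| 1 | 6.0% | 5.1% |

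The favourable-direction column rises because stopping selects looks at which the primary, and anything correlated with it, happens to be high.

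**4. Binding order, but the trial continues and the secondary is retested at 5% at later looks.** Three looks at 1.96 give up to 10.7%.

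**5. The interval and the decision.** A plain 95% interval excludes no effect when |Z| > 1.96; the test rejects when |Z| > 2.2886. They disagree when no look has crossed and the final |Z| lies between the two. Let drift be the expected Z at the final look. At the design effect it is (1/1.5) × √(80 × 40/120) = 0.667 × 5.164 = 3.44. The probability of disagreement is 2.2% at drift 0, 8.4% at 1.5, 10.1% at 2, 9.4% at 2.5 and 4.3% at 3.44.

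**6. The proposed rule.** With one order and each secondary tested at 0.0221 at the look where the primary succeeds, the maximum two-sided error is 5.0%, and 2.5% in the favourable direction. Both maxima remain if the secondary is retested at later looks.

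**The case against.** The best defence is that section 11.4.3 does say the hypotheses are ordered in advance. Read as a strict fixed sequence tested once at stopping, no split of alpha between the secondaries is needed, and two-sided error is about 5%. That is right. A reader might infer from the missing order that family-wise error simply is 10% to 14%, two to three times the intended rate. The text does not support that as a flat statement: those figures need the order to be non-binding or the secondaries to be retested at later looks.

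A reader might also infer that sections 5.2 and 11.4.3 prescribe conflicting test orders. They do not, because neither list is labelled as a test order. The differing lists show only that no order is fixed.

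The favourable-direction figures are maxima over the size of the primary effect. At the design effect they are about 2.7% to 2.9% for correlations of 0.7 to 0.9.

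The interval method is not named, and a repeated interval with 95% overall coverage would also fit the wording. The disagreement in step 5 arises only if a plain interval is used. Likewise, one might read the 5% in section 11.4.2 as the level of the final test, which would make overall alpha 7.2%. Nothing says so, and 0.0221 is exactly the three-look constant for an overall 5%.

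Finally, secondary levels and interval methods are often left to the SAP. That stands for the detail. It does not cover an unconditional claim in the protocol that no adjustment is needed, or the mismatch between one secondary endpoint in the synopsis and three in section 11.4.3.

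**Conclusion.** The point holds as a defect of specification. The inference in section 11.4.3, from a gate on the primary to no need for adjustment, is not valid as written for three endpoints in a three-look design. How much it matters depends on how the gap is filled:

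- up to about 14% family-wise error if the order is not binding and each endpoint is tested at 5% (11% to 14% for mutual correlations of 0.7 to 0);
- about 5% two-sided, at most about 6%, if the order is binding and each is tested once at stopping, with favourable-direction error of up to 3% to 4% at correlations of 0.5 to 0.9 with the primary and about 5% at correlation 1;
- up to about 11% if a secondary is retested at 5% at later looks.

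If plain 95% intervals are used, they contradict a non-rejection at 0.0221 in 4% to 10% of trials with a final-look drift between 1.5 and 3.44. The correlations are assumptions. A high one is plausible for time to improvement, which uses the same WHO scale as the primary.

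Severity is moderate. The protocol describes an exploratory pilot, only secondary claims after a positive primary are affected, and alpha control for the primary is intact if 0.0221 is used at all three looks.

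**What to change.** 1. In section 11.4.3, state one binding test order for the three secondary endpoints, with testing stopped at the first failure. Align the statistical part of the synopsis with it. Either listed order will do statistically.
2. Replace the statement that no adjustment is needed with the rule itself: each secondary is tested at the look where the primary succeeds, at 0.0221, with the same inverse-normal combination.
3. State in section 11.4.2 that 5% is the overall level and that 0.0221 applies at every look, including the final one.
4. For the confirmatory comparisons, report repeated confidence intervals: nominal 1 − 0.0221 = 97.79% per look, 95% overall.

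If no order is wanted and the three are tested only once, a Bonferroni level of 0.05/3 = 0.0167 each keeps the nominal family-wise error at or below 5% (4.9% if independent). The group-sequential part would still need its own rule.

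The cost is wording only. Secondary claims become slightly harder to make and the intervals slightly wider; sample size and conduct do not change.

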
Background and Rationale:
	
Severe acute respiratory syndrome coronavirus 2 (SARS-CoV-2) has spread globally since December 2019 causing a pandemic of Coronavirus disease 19 (COVID-19) in almost all countries worldwide. The clinical spectrum of COVID-19 ranges from asymptomatic carriers to respiratory failure requiring respiratory support in the intensive care unit (ICU). Systemic hyperinflammation is a hallmark of more severe stages of COVID-19 leading to acute respiratory distress syndrome, mechanical ventilation and ultimately death. In this stage, COVID-19 is associated with a decrease in suppressor and regulatory T cell counts and an extensive release of proinflammatory cytokines and biomarkers called a cytokine storm, which is thought to be the major driver of severe pneumonia caused by SARS-CoV-2.
 
No proven or approved effective treatment for COVID-19 infection currently exists. The mechanism responsible for virus-induced hyper-activation of the host immune system remains poorly understood but likely involves several immune cells and inflammatory plasmatic cascades such as the complement and the kinin-kallikrein (KK) system. The complement system (CS) is an integral part of the innate immune system and consists of a number of distinct plasma proteins that act as a first line of defence inducing an inflammatory response after opsonisation of pathogens and dying cells. Previous evidence indicated that an over-activated complement systems, driven by the lectin pathway of complement in particular, seems to contribute to ALI in response to infection with CoV such as SARS-CoV-2 leading to the clinical picture of severe COVID-19 pneumonia and consequently to ARDS.
 
The KK system is a plasmatic cascade that after activation (shear stress of vessels, e.g. during vascular inflammation) and subsequent cleavage of kininogen by kallikrein releases bradykinin. Bradykinin binds to B2-receptors on endothelial cells leading to capillary leakage and angioedema. After enzymatic degradation bradykinin products may also bind to B1-receptors on endothelial cells that are upregulated under proinflammatory conditions and have strong vasopermeable capacity. Although direct evidence is lacking, several facts argue for an involvement of bradykinin in pulmonary angioedema observed in COVID-19, in particular a reduced activity of ACE2 caused by SARS-CoV-2 leading to a relative abundance of bradykinin degradation production with subsequent B1 activation and local pulmonary edema.
 
C1 esterase inhibitor (C1INH) is a member of the serpin superfamily of serine-protease inhibitors and is a strong inhibitor of the CS and KK system among others. Conestat alfa is a recombinant human C1INH, that shares an identical protein structure with plasma-derived C1INH. Although data on C1INH treatment in the context of SARS-CoV-2 infection are lacking, results from previous studies suggest that C1INH treatment may reduce the collateral damage caused by hyperinflammation in human sepsis. The rationale of the current trial is based upon the following assumptions: In the context of COVID-19, conestat alfa treatment may 1) dampen uncontrolled complement activation and collateral lung damage and 2) reduce capillary leakage and subsequent pulmonary edema by direct inhibition of KK system.
 
Hypothesis: Administration of conestat alfa for 72 hours in addition to standard of care (SOC) in patients hospitalized with non-critical SARS-CoV-2 pneumonia (WHO Ordinal Scale Score 3 or 4) will be associated with a reduced clinical severity on day 7 after inclusion and a lower risk of disease progression to ALI and ARDS.

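### The primary test is stratified by baseline WHO score, but the tests named for the gated secondary endpoints are not. They are valid, but inconsistent with the primary and less efficient if the score is prognostic.

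*Protocol*

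**What the plan says.** The primary endpoint, the WHO score at day 7, "will be analyzed by nonparametric logrank test stratified by its baseline values" (Protocol 11.4.2). The synopsis and section 9.2.1 also stratify by baseline.

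Section 11.4.3 lists three secondary endpoints: time to improvement, the proportion with ALI, and the proportion alive without ventilation. Of these it says: "They will be tested only after a significant test of the primary endpoint (a priori ordered hypotheses), therefore, no alpha adjustment is necessary". For quantitative parameters the data are to be "portrayed by Kaplan-Meier plots and compared with the logrank test". For qualitative ones: "Pairwise Chi-Square tests will be carried out in order to compare each of the active treatments to placebo". Neither sentence mentions the baseline score. The synopsis (Statistical Considerations) names only one endpoint for this step, "The secondary endpoint is time to improvement of at least 2 points", and gives no stratified test for it either.

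Section 5.2 counts time to improvement from randomisation, and the event is "an improvement of two points on the seven-category WHO ordinal scale or live discharge from hospital, whichever came first) within 14 days after enrolment". Randomisation is stratified by site only (6.2.1). The synopsis hypothesis describes the target population as "non-critical SARS-CoV-2 pneumonia (WHO Ordinal Scale Score 3 or 4"). Section 7.1, however, exempts high-flow oxygen from the ventilation exclusion, so a baseline score of 5 is possible.

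**The concern.** The sponsor already treats the baseline score as important enough to stratify the primary test by it. The same covariate is known before treatment for everyone, at no extra cost, yet the tests named for the next step of the hierarchy do not use it.

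If patients not on oxygen (score 3) improve faster than those on oxygen (score 4), one pooled logrank test mixes groups with unequal hazards. Treated patients in the fast group leave the risk set first, so the treated patients still at risk become enriched for slow improvers. The treatment contrast then shrinks towards no effect, and power falls. With 40 controls and randomisation stratified by site alone, a chance imbalance in baseline score is not prevented by design either.

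At stake are the power of the gated secondary tests and a clear reading of them beside the primary. If the matter stays open in an open-label trial, there is also a choice between plain and stratified results after the data are known.

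**Working it through.** **The plan's own figure.** The only sample-size figure is for the primary endpoint. With δ = 1 and σ = 1.5 (11.2), two-sided 5% and 80% power, n per arm = 2(1.96 + 0.8416)²/(1/1.5)² = 35.3, so 36. The t-test needs 36.3. Dividing by the Wilcoxon efficiency of 0.955 gives 36.3/0.955 = 38.0, the stated 2 × 38. The protocol states no power, hazard ratio, event count or baseline-score mix for any secondary endpoint, so everything below rests on assumptions.

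**Inputs from the protocol.** 80 versus 40 patients (6.1); daily scoring to day 14 (9.2.2); two-sided 5% with no further adjustment (11.4.3).

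**Assumed inputs.** Exponential times rounded up to whole days; treatment hazard ratio 1.8; a 40/60 split between scores 3 and 4; 70% of controls improved by day 14. For a ratio r between the strata, the score-4 hazard h solves 0.4(1 − e^(−14rh)) + 0.6(1 − e^(−14h)) = 0.70. At r = 2 the control rates by day 14 are 84% and 60% (0.4 × 0.84 + 0.6 × 0.60 ≈ 0.70).

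**Tests compared.** With U the observed minus expected events in the treated arm and V its hypergeometric variance, the plain test is U²/V over all patients. The stratified test is (ΣU)²/ΣV summed over baseline scores. Results from 20,000 simulated trials per row:

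| Hazard ratio between strata | Plain | Stratified | Gain (points) |
|---|---|---|---|
| 1.0 | 76.6% | 75.8% | −0.8 |
| 1.5 | 74.5% | 75.4% | +0.9 |
| 2.0 | 70.3% | 75.1% | +4.8 |
| 2.5 | 65.7% | 74.7% | +9.0 |
| 3.0 | 61.2% | 74.0% | +12.8 |
| 3.5 | 57.7% | 73.6% | +15.9 |

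**Type I error.** The plain test rejects in 4.3 to 4.8% of null trials, so it is not inflated.

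**Sensitivity.**
- Split between scores: over splits from 20/80 to 50/50 the gain is about 2 to 6 points at a ratio of 2 and about 5 to 16 at a ratio of 3. With a 10/90 split it falls to 0.9 and 3.0.
- Significance level: at the Pocock level of 0.0221 the gains at ratios 2 and 3 are 5.6 and 14.1 points.
- Three strata (35/55/10% at scores 3/4/5), daily control hazards 0.20/0.12/0.05: 72% versus 79%. With 0.30/0.12/0.04: 62% versus 78%. With 0.15/0.12/0.08: 79% for both. With no prognostic effect: 81% versus 79%, a loss of 2 points.
- Role of score 5: with the first set of hazards but no score-5 patients (39/61 at scores 3/4), 78.5% versus 80.7%, a gain of about 2 points.

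**Proportions.** Chi-square against Cochran-Mantel-Haenszel with two baseline strata and treatment odds ratios of 0.2 to 0.4: control failure of 15% and 22% gives a gain of 0.2 to 0.7 points; 10% and 50% gives 2.1 to 5.3 points.

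**Does the target differ by baseline score?** Scores 1 and 2 are outpatient states (5.1). Under 5.2 a patient starting at 3 has the event on live discharge. A patient starting at 4 must reach 2, which is also discharge. For these two scores the target is essentially the same. Only a patient starting at 5 can have the event in hospital, by reaching 3.

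**The case against.** The strongest reply is that 11.4.3 never says its tests are unstratified, and that the synopsis leaves detailed methodology to a SAP that is not shown. This stands in part, because the SAP may already stratify. However, the protocol names the secondary tests itself, and the synopsis leaves the choice of tests to the SAP explicitly only for the other outcomes of interest. One section earlier the authors wrote the stratification in where they wanted it. Section 11.4.3 also needs editing in any case: it speaks of several active treatments and a placebo, and the trial has one active arm and no placebo.

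A second reply is that the plain tests are valid, randomisation does not use the baseline score, and the trial is an exploratory pilot. All of this stands, and it limits the point to efficiency and consistency. A plain and a stratified hazard ratio also estimate partly different quantities, so the smaller plain estimate is not simply an error.

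A reader might infer that the endpoint is unequal between strata by construction, because improvement is counted from the baseline score. Section 5.2 does not support that for scores 3 and 4. Section 11.4.3 leaves out live discharge, and read literally it would give scores 3 and 4 different targets; but 4.3, 5.2 and the synopsis all include discharge. The case therefore rests on prognostic strength.

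A reader might also infer a definite loss of 7 to 16 points. That needs a between-stratum ratio of about 2.3 to 3.5 with a fairly balanced split, or an assumed slow score-5 group. The protocol supplies neither.

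**Conclusion.** The point holds as one of efficiency and consistency. The plan conditions its primary test on baseline WHO score and names plain tests for the gated endpoints that follow. Type I error is held, so no result would be invalid.

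For time to improvement, stratifying changes power by about −2 to +5 points if the hazard ratio between baseline strata is at most 2, and by about +5 to +16 points if it is about 3 and the split is not very lopsided. For the two proportions the gain is about 0 to 5 points. These figures rest on an assumed treatment hazard ratio of 1.8 (odds ratios of 0.2 to 0.4 for the proportions), assumed improvement or failure rates and an assumed baseline mix. The direction is firm if the score is prognostic; the size is not known. The balance favours stratifying, because the possible gain is larger than the possible cost.

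**What to change.** In 11.4.3 and the synopsis:

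- Test time to improvement by a logrank test stratified by baseline WHO score, with the same strata as the primary analysis, and report a hazard ratio from a Cox model stratified the same way.
- For the proportion with ALI and the proportion alive without ventilation, replace the chi-square test by a Cochran-Mantel-Haenszel test with a stratified risk difference and its 95% confidence interval.
- Fix in advance that a sparse score-5 stratum is pooled with score 4. If 10% of patients started at 5, it would hold only about 4 controls (0.10 × 40).
- While editing, remove the reference to placebo and align the description of time to improvement with 5.2.

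The cost is a few sentences and no new data, since the score is already recorded on day 0. The downside is about 1 to 2 points of power if the score turns out not to be prognostic. If the SAP already stratifies these tests, it is enough to bring the protocol text into line with it.
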